1. LIST OF ABBREVIATIONS AND RELEVANT DEFINITIONS

Abbreviation/Acronym	Full Wording
AE	Adverse Event
APACHE II	Acute physiology and chronic health disease classification
	system II
ARDS	Acute respiratory distress syndrome
BPsys	Systolic blood pressure
CPAP	Continuous positive airway pressure
CRF	Case report form
EELI	End-expiratory lung impedance
FiO2	Fraction of inspired oxygen
HFNC	High-flow nasal cannula
HR	Heart rate
IMV	Invasive mechanical ventilation
ICU	Intensive care unit
NIV	Non-invasive ventilation
NPO	Nil per os
PaO ₂	Partial arterial oxygen pressure
PEEP	Positive end expiratory pressure
PP	Prone position
SAE	Serious adverse event
SAPS II	Simplified acute physiology score II
SOFA	Sequential Organ Failure Assessment
SP	Supine position
SUSAR	Suspected unexpected serious adverse reaction

Rationale

Acute respiratory failure represents one of the most common causes of intensive care unit admission. Invasive mechanical ventilation (IMV) is the cornerstone support therapy in the most severe patients. Prone positioning is an established evidence-based practice in patients with typical ARDS undergoing IMV, but limited evidence exists in non-ventilated awake patients.

Objectives

To compare awake proning in patients with acute hypoxemic respiratory failure from any cause with standard management.

Hypothesis

Awake prone position in patients with acute hypoxemic respiratory failure is associated with a decreased need for invasive mechanical ventilation.

Study design

Prospective international multicenter randomized controlled trial.

Study population

Adult patients with acute hypoxemic respiratory failure (AHRF) from any cause without respiratory acidosis.

Main study parameters/endpoints

The primary endpoint is the proportion of patients needing invasive mechanical ventilation. Secondary endpoints include the effects of awake proning on the oxygenation parameters, complications, tolerance, length of hospital stay, and 28-day and 90-day mortality.

Nature and extent of the burden and risks associated with participation, benefit, and group relatedness

A significant number of patients under awake proning will eventually require IMV. However, patients will be admitted to the ICU for close monitoring and do not delay intubation when indicated. If the hypothesis proves to be true, there is a potential decrease in intubation and IMV, reducing the risk of complications associated with it, facilitating the early onset of physiotherapy, and early ambulation. All these benefits would hasten recovery, improving short and long-term outcomes. Blood samples will be collected via an existing intravenous catheter or direct vein puncture, but always combined with blood sampling for routine care; the amount of additional blood samples can be considered minimal.

3. INTRODUCTION AND RATIONALE

3.1 Acute respiratory failure

Acute respiratory failure represents one of the most common causes of intensive care unit admission¹. Initial management of the hypoxemic patient should involve immediate use of supplemental oxygen. If the patient fails to achieve adequate oxygenation with conventional supplemental oxygen, high-flow nasal cannula (HFNC) oxygen or non-invasive positive pressure ventilation (NIPPV) may be used. If patients fail to improve with the non-invasive methods after a time-limited trial or worsen, timely endotracheal intubation should be considered to avoid any harm.

3.2 Complications of mechanical ventilation

Even though mechanical ventilation is a life-saving strategy in patients with respiratory failure, mechanical ventilation is associated with serious complications. These complications may be related to the direct mechanical effects of the intrathoracic pressures generated by the ventilator, to alveolar and systemic inflammation, or to neural stimulation². Experimental^{3–5} and clinical⁶ studies show that MV has the potential to aggravate or even initiate lung injury (so-called ventilator-associated lung injury, VALI). Patients undergoing MV, sedation with or without paralysis are often required, especially for patients with shock or ARDS or those "fighting the ventilator." ⁷ The use of sedative agents may unduly prolong MV's duration, precluding mobilization, promoting muscular deconditioning, and leading to detrimental short-and long-term outcomes^{8,9}.

3.3 Prone position in ARDS

Prone positioning (PP) was first recognized for its ability to improve oxygenation and was historically used in the 1970s to improve gas exchange and salvage therapy for refractory hypoxemia¹⁰. A seminal multicenter trial and subsequent meta-analyses have made a compelling case that prone positioning in selected patients with severe acute respiratory distress syndrome (ARDS) early in their course improves survival¹¹. This survival benefit is likely mediated by reduced VILI, as regional differences in lung aeration, compliance, and shear strain are minimized^{12,13}.

3.4 Prone position in spontaneously breathing patients

The benefit of prone positioning may not be restricted to invasively ventilated patients. At least, in theory, non-intubated patients could also benefit from being placed in the prone position^{14,15}, also called "awake proning."

Theoretically, PP benefits may concern spontaneous breathing patients, in whom it could contribute to the success of the non-invasive strategy. Current evidence comes from few studies, mostly case reports and single-center observation case series^{15–17} involving patients undergoing NIV or high flow oxygen therapy and suggesting suitable patients' tolerance, significant improvement in oxygenation during the procedure, and no increase in nurse workload. It has been described that the median duration of prone positioning is 3 (2-4) hours with no other respiratory or technical complications, such as displacement of indwelling catheters, facial edema, pressure sores, pressure neuropathies, compression of nerves, and retinal vessels or vomiting¹⁶.

A rapidly growing number of observational studies describe the use of awake proning in patients with acute respiratory failure in whom hypoxemia is refractory to simple supplementary oxygen^{18–24}.

It is crucial to note that there is no randomized trial evidence for the effect of awake proning in patients with acute respiratory failure so far. The number of studies investigating awake proning is rapidly growing, but thus far, randomized clinical trials remained absent.

Given its tolerability and few complications in spontaneous breathing patients, the prone position could be adjuvant therapy in acute respiratory failure patients. It may avoid the need for invasive mechanical ventilation and its side effects.

4. OBJECTIVES AND HYPOTHESIS

4.1 Objectives

The proposed randomized controlled trial aims at comparing the application of the prone position in spontaneously breathing patients with acute hypoxemic respiratory failure versus standard treatment on the rate of invasive mechanical ventilation, as well as determining the effects of oxygenation, safety, length of ICU, and hospital stay and, mortality at day 28 and day 90. Spontaneous breathing is defined as patients without invasive mechanical ventilation or extracorporeal respiratory support system.

4.2 Hypothesis

We hypothesize that in adult patients with acute hypoxemic respiratory failure from any cause and spontaneous breathing, the prone position application decreases the intubation rate compared to the best standard of care.

5. STUDY DESIGN

Multicenter, international, randomized controlled trial on acute hypoxemic respiratory failure patients with a respiratory rate of more than 25 breaths per minute, $SpO_2 < 94\%$ and FiO_2 of at least 40% or more by either Venturi facemask, HFNC or NIV/CPAP and, absence of decompensated respiratory acidosis.

6. STUDY POPULATION

6.1 Population (base)

We intend to recruit acute hypoxemic respiratory failure patients with a respiratory rate of more than 25 breaths per minute, $SpO_2 < 94\%$ and FiO_2 of at least 40% or more by either Venturi facemask, HFNC, or NIV/CPAP and, absence of decompensated respiratory acidosis during two years. Currently, we expect about 35 centers to participate in the trial.

Demographic data and clinical characteristics on screened patients, regardless of enrolment criteria match, will be recorded (registry). We will randomize 714 patients admitted to the participating centers' intensive care units and expect each participating center to randomize at least 25 patients who meet all inclusion criteria.

6.2 Inclusion criteria

- >18 years
- Acute respiratory failure from any cause
- Admitted to a participating ICU
- Written informed consent

6.3 Exclusion criteria

- Presence of any contraindication to prone position (APPENDIX i)
- The patient meets the criteria for intubation (APPENDIX ii)
- Participating in other interventional studies with the same primary outcome
- Receiving comfort care only
- Pregnancy

6.4 Sample size calculation

The initial sample size calculation was based on our primary hypothesis and primary study outcome. The required sample size was calculated using data from a multicenter randomized controlled trial reporting intubation rate in patients with acute hypoxemic respiratory failure with a PaO₂/FiO₂ ratio less than 200 using HFNC²⁵.

These calculations indicated that 322 patients would be required per group, assuming a twosided significance level of 0.05 and a power of 80%, to detect the expected difference in the

rate of mechanical ventilation between the prone position group of 24 % and the standard treatment group of 34 % (risk ratio of 0.70). Assuming a dropout rate of 10%, **a total of 714 patients** (n= 357 per group) were planned to be included in the study.

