7.2.1 Randomization

Randomization procedure

Randomization will be performed using a dedicated website and will be balanced per center. *Randomization arms*

Central randomization with the use of a permutated-block randomization list (block length 6) will be used. Participants will be allocated to the prone position or standard care on a 1:1 ratio. At each site, at least two investigators will be involved: one who will be aware of the allocated intervention and collect the data; the other will remain blinded to the interventions and evaluate the outcomes.

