8.2 Analysis

The goal of the primary outcome is to quantify the effect of prone position versus the standard treatment upon the need for invasive mechanical ventilation during the first fourteen days after randomization.

Interim analyses for efficacy and futility will be conducted at 50% (N= 357), 75% (N= 476), and 100% (N= 714) of the planned enrollment, as needed, using a non-binding group sequential design with gamma spending functions (gamma = -4 for each of alpha and beta).

The table below shows the alpha and beta spent over the trial, z-statistic boundaries for efficacy and futility, and boundary-crossing probabilities under the alternative hypothesis (H1). The corresponding P-value boundaries for efficacy (futility in parentheses) at the 1st, 2nd and final looks, respectively, are P≤ 0.006 (P>0.82), P≤ 0.015 (P>0.35), and P ≤ 0.044 (P>0.044). The Figure below displays the z-statistic boundaries for efficacy/harm and futility as a function of accrued sample size.

For the primary efficacy analysis rates of invasive mechanical ventilation will be compared between the two intervention groups, and the odds ratio relative risks with corresponding 95% confidence levels interval will be calculated using logistic regression analysis.

With regard to the remaining parameters: Normally distributed variables will be expressed by their mean and standard deviation; non-normally distributed variables will be expressed by their medians and interquartile ranges. Categorical variables will be expressed as n (%).

Student's t-test will be used to test groups of continuous normally distributed variables.

Conversely, if continuous data is non-normally distributed, the Mann-Whitney-U test will be used. Categorical variables will be compared with the Chi-square test, Fisher's exact tests, or, where appropriate, as relative risks. Time-dependent data will be analyzed using a proportional hazard model adjusted for possible imbalances of patients' baseline characteristics.

COVID-19 status of patients will be taken into account and analyzed in the study to find any

differences in the primary and secondary outcomes between COVID-19 and non-COVID-19 patients.

A stratified analysis will be done by the device used (HFNC, BIPAP, CPAP, and their interfaces).

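### The 80% power in section 6.4 belongs to a single-look test; with the interim looks of section 8.2, 322 evaluable patients per group give about 78 to 79.5%

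*Protocol*

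**What the plan says.** Section 6.4 (Sample size calculation) presents an initial calculation: "322 patients would be required per group, assuming a twosided significance level of 0.05 and a power of 80" per cent. The effect to be detected is the difference in the "rate of mechanical ventilation between the prone position group of 24 % and the standard treatment group of 34 % (risk ratio of 0.70"). Ten per cent dropout is then allowed for, which gives 714 patients, 357 per group. The section mentions no interim analyses.

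Section 8.2 (Analysis) plans looks at "50% (N= 357), 75% (N= 476), and 100% (N= 714) of the planned enrollment", "using a non-binding group sequential design with gamma spending functions" with gamma = -4 for both alpha and beta. The P-value bounds at the first two looks, with futility in parentheses, are "P≤ 0.006 (P>0.82), P≤ 0.015 (P>0.35"). At the last look efficacy requires P ≤ 0.044. Section 8.2 also refers to a table of boundary-crossing probabilities under the alternative. That table is not in the text available for this review.

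**The concern.** A sequential test that spends part of its alpha early, tests at 0.044 rather than 0.05 at the end and may stop for futility has less power than a single test at 0.05 with the same number of patients. If 322 comes from the single-look formula, the 80% in section 6.4 is not the power of the confirmatory test in section 8.2, and the two sections rest on different calculations. At stake is the accuracy of the stated power. The type I error is not affected.

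**Working it through.** **Inputs.** Section 6.4: rates 0.34 and 0.24 (difference 0.10, mean 0.29), two-sided alpha 0.05, power 80%, 322 evaluable and 357 enrolled per group. Section 7.2.1: 1:1 allocation. Section 8.2: looks, gamma = -4, P bounds 0.006 / 0.015 / 0.044 for efficacy and 0.82 / 0.35 for interim futility. The futility P values are read as two-sided.

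**1. Reproduce the protocol's figure.** Single-look power with pooled variance under the null is

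Φ{[0.10·√n − 1.96·√(2·0.29·0.71)] / √(0.34·0.66 + 0.24·0.76)}.

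At n = 322: (1.7944 − 1.96 × 0.6417) / 0.6378 = 0.841, so power = 80.0%. The 322 is therefore a single-look number with no allowance for interim looks.

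**2. Check that section 8.2 is read correctly.** Gamma = -4 spending of one-sided 0.025 at 50%, 75% and 100% gives z = 2.750, 2.432 and 2.012. These are two-sided P = 0.0060, 0.0150 and 0.0442, which match the printed efficacy bounds.

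**3. Power of the sequential design.** The drift (expected z at the final look) is 0.10 / √(V/n). V is 2·0.29·0.71 = 0.4118 (pooled) or 0.34·0.66 + 0.24·0.76 = 0.4068 (unpooled).

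- n = 322: drift 2.80 pooled, 2.81 unpooled.
- n = 357: drift 2.94 pooled, 2.96 unpooled.

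Numerical integration with the printed bounds and looks at 50/75/100% gives the following (range: pooled to unpooled).

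| Evaluable per group | Futility ignored | Futility followed |
|---|---|---|
| 322 (10% loss) | 79.0–79.5% | 78.1–78.6% |
| 357 (no loss) | 83.0–83.5% | 82.1–82.6% |

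Binomial simulation with 1,000,000 trials per scenario agrees: 79.3% and 78.4% at 322; 83.2% and 82.4% at 357.

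**4. Which sample size do the printed boundaries fit?** Gamma = -4 with beta = 0.20 spends 0.0238 of beta by the first look and 0.0712 by the second. Suppose futility is declared when |z| falls below the bound. The design then reaches 80% power at a drift of about 2.86, with futility bounds P = 0.82 and P = 0.35, which are the printed values. The sample size for that drift is

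n = 0.4118 × (2.86 / 0.10)² = 336.8, or about 337 evaluable per group (pooled variance).

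Loss that 357 per group can absorb: 1 − 337/357 = 5.6%. Section 6.4 assumes 10%.

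**The case against.** The strongest reply is that nothing in section 6.4 is miscalculated. It calls the calculation initial, lists its assumptions and makes no claim about sequential power. Section 8.2 sets its looks against 714 enrolled patients, and section 8.2 also specifies intention-to-treat with all patients as randomized. With a 14-day intubation outcome, loss may be well below 10%; if there is none, power is 82% or more. Futility is non-binding, so the sponsor may ignore it and lose at most about one point at 322 per group. The table of crossing probabilities under the alternative may already give the sequential power. All of this stands, and it is why the point is minor. It does not make the 80% at 322 per group the power of the planned test, and section 6.4 is where a reader looks for that power.

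Three stronger readings are tempting, and the documents do not support them.

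- *Power falls to about 77%, a loss of more than two points.* Figures of 77.5 to 78.0% appear only when bounds computed for 75% of the information are applied at N = 476. But 476/714 = 66.7%. The named spending function would give a look at 66.7% its own bounds, and power at 322 per group is then about 78.5 to 79%. The mismatch between 75% and N = 476 is a separate defect and should not be counted again here.
- *The boundaries are incoherent.* They are not. Step 4 shows that they fit an 80%-power sequential design; that design simply needs about 337 per group rather than 322.
- *The trial is underpowered and must enrol more.* Power is above 80% at the planned enrolment unless loss exceeds about 5 to 6%.

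**Conclusion.** The point holds and is small. The 322 per group in section 6.4 carries 80% power only for a single test at two-sided 0.05. With the design in section 8.2 the loss at 322 is about 0.5 to 1 point if futility is ignored, and about 1.5 to 2 points if it is followed at 50% and 75%. The printed boundaries and the 322 come from different calculations, and enrolment of 357 per group bridges them only at a loss of about 5 to 6% or less.

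This rests on the protocol's own rates, on beta = 0.20 (the only power it states), on futility P values read as two-sided, and on looks at 50% and 75%. Treating an unfavourable direction as futility as well lowers power by about 0.1 point. The unseen table could show that sequential power has been reported, but it would not alter what 322 represents. A reader should not infer from the quoted sentence that the trial cannot meet its objective.

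**What to change.** In section 6.4, state that 322 per group is the single-look requirement and excludes inflation for interim analyses. Add that, with the planned looks, power is about 78 to 79% at 10% dropout and about 82 to 83% if all 714 patients are evaluable. Make these figures agree with the table of crossing probabilities in section 8.2 and refer to it. Once the separate mismatch between 75% and N = 476 is settled, compute the boundaries and the power together from one set of look sizes.

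The cost is one or two sentences and one rerun of the design calculation. Enrolment, the test and the error rate do not change; the power quoted at 10% dropout becomes slightly less favourable.

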7. METHODS

7.1 Study parameter/endpoints

7.1.1 Main study parameters/endpoint

• Rate of invasive mechanical ventilation during the first fourteen days of enrolment

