7.2.2 Prone position

Supine to Prone

The patient will be placed in the prone position for at least 2 hours, which may be prolonged if the patient is comfortable or interrupted if the patient presents any criteria for prone position discontinuation (APPENDIX iii).

During the maneuver, FiO_2 will be increased by 25% above the baseline and then gradually decreased to the baseline value within the first 10 minutes of prone positioning, targeting for a SpO₂ of 94-96%. The total time of the prone position will be recorded.

The maneuver will be performed by two operators and the attending physician, while in patients with impaired mobility, up to 5 operators will be required. Skin protections will be used to avoid pressure sores. Also, the application of cushions will enhance patient tolerance to the

maneuver.

Arms can be at the side, in swimmer position, and can be moved to the patient's comfort. Vitals, SpO₂, and SpO₂/FiO₂ will be measured before and at the end of the prone position session.

Enteral or oral feeding will be interrupted 1 hour before prone positioning and re-established when the patient is in the semi-recumbent supine position.

Opiates, benzodiazepines, or alpha-2-adrenoceptor agonists can be used during the maneuvering at non-sedative doses to enable adaptation to the maneuver or treat anxiety symptoms related to respiratory failure.

If non-tolerance to the prone position, all clinical data will be collected, and the patients will be promptly rotated in the supine position. The reasons for prematurely unproning the patient will be accurately recorded. In case of sudden worsening of the oxygenation impairment or hemodynamics, 100% FiO₂ will be set, and the patient will be promptly positioned in the supine semi-recumbent position.

Prone to Supine

After the prone position period, the patient will be rotated to the semi-recumbent supine position for at least 2 hours and a maximum of 4 hours. This 2-hour time frame will depend on nursing availability, need for hygiene, complementary explorations, or diet.

As described previously, for the procedure, FiO_2 will be increased up to 25% above the baseline and then gradually decreased to the baseline value within the following 10 minutes targeting a SpO₂ of 94-96%.

Vitals, SpO_{2} , and SpO_{2}/FiO_{2} will be measured before and at the end of the supine position session.

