7.2.3 Standard management

The standard management of patients with acute hypoxemic respiratory failure will be done according to the usual practices of each participating center.

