The patients will be assessed daily between the third and the fourteenth day after the protocol and the last day before discharge from the ICU and the hospital. Discharge from critical care is defined as the first discharge to a medical or surgical ward in the hospital or another hospital; a transfer between ICUs is not considered a discharge from critical care. Hospital discharge is the first date that the patient is discharged to home/community; a transfer between hospitals is not considered as a hospital discharge. Clinical data and the presence of complications will be registered and the date of the development of any complication documented (see APPENDIX vi). The following variables will be collected:

- Continuation of prone position
- Continuation and time spent under the non-invasive respiratory support device
- Day and time of unassisted breathing; i.e., no ventilatory support and use of conventional supplemental oxygen or room air
- Chest X-ray
- Need for invasive mechanical ventilation
- Any need for anti-arrhythmic and vasoactive medication; if yes: specify
- Date of ICU discharge
- Date of hospital discharge

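### No common intubation threshold applies to both arms after randomization, although the sole confirmatory endpoint rests on a decision to intubate that is very probably unblinded

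*Protocol*

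**What the plan says.** Section 7.1.1 defines the primary endpoint as the "Rate of invasive mechanical ventilation during the first fourteen days of enrolment". The summary words it as a need: "The primary endpoint is the proportion of patients needing invasive mechanical ventilation". Section 8.2 also speaks of the effect "upon the need for invasive mechanical ventilation during the first fourteen days after randomization", and makes this the only confirmatory analysis.

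Intubation criteria are set out in Appendix ii. The body text invokes them once, as an exclusion at entry: "The patient meets the criteria for intubation (APPENDIX ii" (6.3).

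On who acts at the bedside, 7.2.2 says: "The maneuver will be performed by two operators and the attending physician". In the control arm, management "will be done according to the usual practices of each participating center" (7.2.3). Section 7.2.1 provides two investigators per site. One knows the allocation and collects data; "the other will remain blinded to the interventions and evaluate the outcomes".

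On data, the post-protocol list in 7.2.4 has the item "Need for invasive mechanical ventilation" without reference to Appendix ii. Section 7.1.2 lists intubation among the serious adverse events, and Appendix vi asks for a clinical narrative on each event.

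**The concern.** Position cannot be masked at the bedside. Whether a patient was ventilated by day 14 is hardly open to interpretation; the judgment lies in the earlier decision to intubate. When that decision is open-label, the main feasible protection is a shared reference for making it. The protocol contains one but does not carry it past enrolment.

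Differences in threshold between centers are not the worry, because randomization is balanced per center. What matters is a threshold that differs between arms within a center. A clinician might wait longer with a patient who is being proned, or intubate earlier when a proning session fails. The first would exaggerate a benefit; the second would hide one. A site could comply fully with the protocol while doing either.

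**Working it through.** **1. Where Appendix ii is applied**

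- Invoked: 6.3 (entry exclusion).
- Not invoked: 7.1.1 (endpoint), 7.2.2 (prone procedure), 7.2.3 (standard management), 7.2.4 (data), 8.2 (analysis).
- The other appendices are linked where they are used on study: iii in 7.2.2, iv in 7.1.2, v in 7.2.4, vi in 7.2.4 and 8.3.
- The only other instruction on intubation timing, in the summary, is a general one not to put off an indicated intubation. It cites no criteria.

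**2. The plan's own figure**

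Inputs (6.4): 34% versus 24%, two-sided alpha 0.05, power 80%. Pooled-variance formula:

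n = [1.960 × √(2 × 0.29 × 0.71) + 0.842 × √(0.34 × 0.66 + 0.24 × 0.76)]² / 0.10² ≈ 322 (323 when rounded up).

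The stated 322 per group reproduces. Dropout: 322 / 0.90 = 357.8, against the stated 357 per group.

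**3. Illustration of a threshold that differs by arm**

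Assumptions, none from the documents: no true effect, 34% in controls, and a share s of prone-arm intubations avoided through day 14. The prone rate is then 0.34 × (1 − s). With pooled standard error se0 and unpooled se1, and d the difference between arms:

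P(reject) = Φ((d − 1.96 se0)/se1) + Φ((−d − 1.96 se0)/se1).

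For s = 10% and n = 357: d = 0.034, se0 = 0.0350, se1 = 0.0350, giving 0.161 + 0.002 = 0.163.

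| s | Prone rate | Patients (n=322; 357) | P(reject) (n=322; 357) | Three-look simulation |
|---|---|---|---|---|
| 0% | 34.0% | 0 | 0.050; 0.050 | 0.051 |
| 5% | 32.3% | 5.5; 6.1 | 0.074; 0.077 | 0.077 |
| 10% | 30.6% | 10.9; 12.1 | 0.152; 0.163 | 0.160 |
| 15% | 28.9% | 16.4; 18.2 | 0.286; 0.311 | 0.305 |
| 20% | 27.2% | 21.9; 24.3 | 0.465; 0.505 | 0.497 |

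The simulation (400,000 runs) uses the looks and nominal p-values printed in 8.2 (N = 357, 476, 714; 0.006, 0.015, 0.044), efficacy and harm boundaries only. Placing the second look at 536 (75% of 714) changes no entry by more than 0.002.

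In the opposite direction, if a true 10-point effect is shrunk by 2 points, power at 322 per group falls from 80% to 60%; by 3 points, to 49%.

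**4. Load and precision of the fix**

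Expected intubations at 357 per arm: 0.34 × 357 = 121.4 control and 0.24 × 357 = 85.7 prone, total 207. With no effect, 2 × 121.4 = 243.

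Half-width of the 95% interval for the by-arm difference in the share q meeting criteria: 1.96 × √(q(1 − q)(1/a + 1/b)), with q assumed.

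| Intubations (a, b) | q = 0.7 | q = 0.8 | q = 0.9 |
|---|---|---|---|
| 121, 86 | 12.7 | 11.1 | 8.3 points |
| 121, 121 | 11.5 | 10.1 | 7.6 points |

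**The case against.** The strongest case is that the protocol already has what is feasible in an open-label trial: balanced randomization per center, a blinded outcome evaluator and a blinded analysis. Appendix ii is headed as intubation criteria, its wording on persistence and worsening describes a course over time, and every site must apply it to every patient before randomization. On this view the gap is one of drafting. It may well be that on-study use was intended, but the text never says so, and none of the listed protections acts on the decision to intubate.

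Three further objections stand and limit the point:

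- A reader might infer from the word *need* that the endpoint is undefined. It is not. Sections 4.1, 4.2, 6.4, 7.1.1 and 8.2 all count intubation or receipt of invasive ventilation, and *need* is loose wording.
- A reader might infer that nothing structured is collected on the grounds for intubation. Respiratory rate and SpO₂ are recorded during the 48-hour protocol (7.2.4), and SpO₂ and physical examination on days 1-7 (Appendix v). These are not timed to intubation and leave out pH, secretions and Glasgow score. The electronic case report form is not shown and may record more.
- Appendix ii has only respiratory and neurologic items. Scored literally, justified hemodynamic or procedural intubations would count as off-criteria, so overrides must carry a reason.

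The analysis plan is not at hand. It could add a sensitivity analysis, but rules for intubation and bedside data capture belong in the protocol.

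**Conclusion.** The point holds as a missing link. The criteria exist, but the protocol does not make them the reference in either arm after randomization, while the only confirmatory endpoint depends on a decision very probably made with knowledge of the allocation. *Very probably* is as far as the text goes: no section says who decides.

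A reader might infer from the rejection probabilities that the trial has a false-positive risk of 15% or more. The documents do not support that. Nothing in them shows that thresholds would differ by arm, or in which direction, and the shares avoided are assumptions. The illustration also requires intubations to be avoided through day 14; one that is merely delayed but still occurs by day 14 counts as an event. Small shifts do little (7-8% at 5% avoided), and at 10% avoided about 85% of such trials would still not reject. The figures show only that a moderate within-center shift could matter.

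This should be fixed because it concerns the sole confirmatory result and the remedy is cheap. Confidence is moderate.

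**What to change.** State in 7.2.2 and 7.2.3 that Appendix ii is the reference for intubation in both arms through day 14. Allow clinician override and require its reason, including hemodynamic, airway-protection or procedural reasons, which Appendix ii does not list. For each intubation, record the date, time and criteria met, and report these by arm as a descriptive check.

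The cost is one sentence in each of two sections and a short form for roughly 207-243 intubations, about 3 in 10 of the 714 patients, with no extra staff. Discretion is documented, not removed, and some criteria will still be charted by unblinded staff. The check has a precision of about ±10 to 11 points if 80% of intubations meet criteria, so it can show only a large imbalance. It sees intubations made below the reference, not those withheld. The main gain is the shared threshold set in advance.
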